STUDY PROTOCOL PLAN AND STADISTICAL ANALYSIS PLAN (SAP)

UNIVERSITY CEU CARDENAL HERRERA

Principal investigator: [name] [name]

TITLE: Stabilometric and baropodometric evaluation of osteopathic scaphoid tug manipulation

Research and Ethics Committee of CEU Cardenal Herrera University Number: CEEI22/322

NCT ID: [not yet assigned]

DATE: 10/13/2022

STUDY PROTOCOL PLAN

Objectives:

The objectives of our study have been the following:

General:

The main objective of this study was to evaluate, in healthy individuals, the stabilometric and baropodometric modifications recorded after an osteopathic tug manipulation of the scaphoid, neurophysiologically related to the static and postural control system of the body (exocaptor input) and biomechanically as a structure that communicates the body with the ground

Specific:

To evaluate by means of stabilometry the modifications in the variables of oscillation in X axis, oscillation in Y axis and ellipse area between the intervention group and the control group after the performance of an osteopathic scaphoid tug manipulation or a placebo technique respectively and to evaluate the results.

To assess the changes in the variables % weight load, bearing surface and maximum pressure in both feet by baropodometry between the intervention group and the control group after the application of a scaphoid tug manipulation or a placebo manoeuvre respectively and to compare the results.

To study and compare the results of the stabilometric and baropodometric variables obtained between the subgroups of the intervention group after the osteopathic tug manipulation of the scaphoid: audible and non-audible manipulation and to compare the results.

Volunteers who want to participate in the study will read the general information of the study and sign the informed consent to participate in the study.

Once the informed consent has been read and delivered, the evaluator will check that they meet the inclusion criteria. After the data collection, a randomization (Epidat V4.0) of the selected subjects will be carried out to assign them to one of the intervention groups.

The sequence of the study was as follows:

1. Information about the study to the subjects likely to participate.
2. Provision of the informed consent form to be read and signed by the patient (appendix I).
3. The evaluator will take the data for the clinical history.

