4. The assessor will evaluate the mobility of the scaphoid of the right foot and will verify that it is in osteopathic external rotation dysfunction, if this dysfunction is not present, the subject will be excluded from the study.
5. The assessor shall collect data to obtain the independent variables of stabilometry and baropodometry by means of standardised recording on the measurement platform in a standardised room for this purpose.
6. The patient will go to an adjoining room with the auditor to carry out the randomisation process (random number generator) and thus classify the patient into the experimental or control group.
7. Implementation of the intervention: in the experimental group, the scaphoid tug technique will be performed. In the control group patients a sham technique will be applied.
8. The patient will return to the assessment room with the assessor for data collection to obtain the variables of stabilometry and baropodometry by standardised recording on the measurement platform, as was done previously.

9. Collection of data on computer support by means of a database.

Baropodometric and stabilometric assessment:

Stabilometric and baropodometric assessment was carried out using this sequence:

- The subject should be dressed in comfortable clothing and barefoot on the measuring platform.
- Upright position with arms relaxed.
- Placement of a wooden pattern for the positioning of the patient's feet, instructing him to place his feet against the edges of the wooden pattern and the heels subsequently contacting the guide (heel separation 2 cm and separation of 30°). Once positioned, the wooden pattern is removed.
- Stabilometric measurements and recordings: this shall be taken before the baropodometric recording, with a recording time of 51 seconds 2 tenths (standardised and consensual recording time).
- Measurement and baropodometric recording: this recording shall be performed after the stabilometric recording while maintaining the same posture.

The stabilometric evaluation will be carried out with the eyes open, as only the foot sensor will be evaluated in the study.

The stabilometric scan of this study will provide the following data:

- Oscillation about the X-axis.
- Y-axis oscillation.
- Area of the ellipse.

The static baropodometric scan of this study shall provide the following data:

- Area of support of the foot.
- Percentage of body load supported by each foot.
- Point of maximum plantar pressure.

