A descriptive and exploratory analysis of the variables of interest will be carried out in order to detect anomalous cases and to clean the database. The assumption of normality will be tested with the Shapiro-Wilks test in combination with an analysis of Q-Q and Q-Q normality plots without trend. The assumption of equality of variances will be tested with Levene's test. A repeated measures ANOVA model will be applied with the variable of interest as the within-subjects factor (three levels) and the group as the between-subjects factor (two levels). Bonferroni correction will be used for two-to-two comparisons. Effect size will be estimated with Cohen's d (1988) where values around 0.20 will be considered small effect size; around 0.50 moderate and 0.80 or higher, large. The statistical analysis software used will be IBM SPSS Statistics 24.0 (SPSS Inc. IBM Company, 2010) and a 95% confidence interval will be applied in all statistical tests.

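### The SAP's only model has an undefined three-level within-subjects factor, but the protocol describes two recordings, so the before/after treatment test is not specified

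*Combined protocol and SAP*

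**What the plan says.** The section headed Statistical Analysis Plan (SAP) contains a single inferential model: "A repeated measures ANOVA model will be applied with the variable of interest as the within-subjects factor (three levels"), together with "the group as the between-subjects factor (two levels"). It adds that "Bonferroni correction will be used for two-to-two comparisons" and that effect size will be expressed as Cohen's d. It does not name the three levels or say which comparisons the correction and the effect size refer to.

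The numbered study sequence in the protocol sets out the measurements. Step 5, before randomisation: "The assessor shall collect data to obtain the independent variables of stabilometry and baropodometry by means of standardised recording on the measurement platform". Step 8, after the technique: "The patient will return to the assessment room with the assessor for data collection to obtain the variables of stabilometry and baropodometry", in the same way as before. Step 9 is entry into a database. No further recording or follow-up is described.

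The first specific objective is to evaluate "the modifications in the variables of oscillation in X axis, oscillation in Y axis and ellipse area between the intervention group", compared with controls, once the manipulation or placebo has been applied. The second asks the same of the baropodometric variables. The third compares results "between the subgroups of the intervention group after the osteopathic tug manipulation of the scaphoid: audible and non-audible manipulation".

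**The concern.** The objectives call for a comparison between groups of a before/after change. The analysis section names no term that makes this comparison, and the one factor that could carry it has a level count that does not match the design. Three readings are possible, and each needs something that is not written:

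- **The levels are time points.** A third occasion is needed, and none is described.
- **The levels are the three outcomes of one scan.** Quantities in different units become repeats of one measure. The model has no before/after term unless change scores are entered, and the SAP does not say that they are.
- **The two counts were swapped** (two occasions; control, audible and non-audible groups). This contradicts the two-level group factor.

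What is at stake is pre-specification. These readings give different tests, and the choice among them would be made with the data in hand. The Bonferroni sentence and Cohen's d do not settle it, because neither is tied to named levels, occasions or groups.

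**Working it through.** **1. Level count.** The SAP states 3 within-subject levels. Counting recordings in steps 1 to 9 of the sequence gives step 5 and step 8, so 2. The stated figure is not reproduced from the described occasions. The number 3 does appear elsewhere: three stabilometric outcomes (X oscillation, Y oscillation, ellipse area) and three baropodometric outcomes (support area, percentage load, maximum pressure). No text links either set to the ANOVA factor.

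**2. What the count changes.** With k within-subject levels and g = 2 groups, there are k(k−1)/2 pairs of levels, the Bonferroni threshold is 0.05 divided by that number, and the group-by-within interaction has (k−1)(g−1) numerator degrees of freedom. The 0.05 is implied by the SAP's 95% confidence level.

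| | k = 3 (SAP) | k = 2 (study sequence) |
|---|---|---|
| Pairs of levels | 3 | 1 |
| Bonferroni threshold | 0.05/3 = 0.0167 | 0.05 (nothing to correct) |
| Interaction numerator df | 2 | 1 |

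**3. What the two-occasion model would test.** With k = 2, the group-by-time F equals the square of the t statistic on change scores. On simulated pre/post data both were 5.874. This 1-df test answers the objective for one outcome, and the SAP does not name it. ANCOVA is not the same test: on the same simulated data the estimate was 0.571 against 0.551, and p was 0.004 against 0.019.

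**4. What happens if the outcomes are the levels (illustration only).** The documents give no sample size, SD, correlation, effect or unit, so every input here is assumed. On this reading the group main effect is a t-test on each participant's sum X + Y + area. Its noncentrality is δ/σ × √(n/2), where n is the number per arm, δ is the group difference in the sum and σ is the SD of the sum.

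Central case: 30 per arm, X and Y SD 3 mm, area SD 60 mm², all correlations 0.5, d = 0.8 on X and Y, no effect on area. Then δ = 0.8×3 + 0.8×3 = 4.8.

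- Area in mm²: σ² = 9 + 9 + 3600 + 2×0.5×(9 + 180 + 180) = 3987, so δ/σ = 0.076, noncentrality 0.294 and power 0.060.
- Area in cm² (SD 0.6): σ² = 9 + 9 + 0.36 + 2×0.5×(9 + 1.8 + 1.8) = 30.96, so δ/σ = 0.863, noncentrality 3.341 and power 0.907.

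A simulation of this case (4000 replicates) gave 0.057 and 0.908 for the main effect. For the group-by-variable interaction it gave 0.052 and 0.937 with the Greenhouse-Geisser correction.

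The table gives the range over 20, 30 and 50 per arm, correlation 0.2, 0.5 and 0.8, and area SD 20, 60 and 150 mm², with no effect on area:

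| Effect on X and Y | Area in mm² | Same data, cm² |
|---|---|---|
| d = 0.8 | 0.051–0.195 | 0.561–0.999 |
| d = 0.5 | 0.050–0.105 | 0.262–0.885 |

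The gap is not universal. With d = 0.8 on all three outcomes in the central case, main-effect power is 0.89 in mm² and 0.95 in cm².

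**The case against.** The best defence is that the sentence is loosely worded. The SAP first uses the plural for the variables to be explored, then the singular in the model, which may mean one outcome at a time, measured repeatedly. The protocol supplies the pre/post structure, and in a two-group pre/post design the group-by-time interaction is the conventional treatment term. A three-level time factor could not be fitted to two recordings, so the analyst has less freedom than the concern suggests. On this view the defect is a wrong count and an unnamed factor.

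This is a plausible guess at the intention, but it does not rescue the text: the level count is still wrong, the time factor is still missing, and the treatment term is still left to convention.

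Four narrower points stand, and they limit how the evidence should be used:

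- The power figures rest wholly on assumed inputs and apply to one reading only. The large gap also needs no effect on area.
- The 3-against-1 Bonferroni count applies only if pairs of within-factor levels are meant, which the SAP does not say.
- Nothing in the text positively supports the swapped-counts reading.
- A remedy that fixes two levels must allow for a third recording that was intended but left out.

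**Conclusion.** The concern holds. The only inferential model in the plan specifies three within-subject levels, the protocol describes two recordings, and no text defines the levels or names the treatment contrast. This is a stated rule that conflicts with the design, so it is wrong as written and not merely short on detail. It must be fixed before analysis because it governs the main comparison for every outcome.

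The conclusion rests on the 3-against-2 mismatch and the missing treatment term, and these need no assumption. The Bonferroni count is secondary. The unit-dependence figures show only why outcomes should not serve as levels of one factor; they say nothing about this trial's actual power.

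**What to change.** First confirm whether two or three recordings are planned. If two, replace the model sentence with text such as:

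> For each outcome separately, a repeated-measures ANOVA will be fitted with time (pre, post; two levels) as the within-subjects factor and group (manipulation, sham; two levels) as the between-subjects factor. The group-by-time interaction, which is identical to a t-test on change scores, is the treatment test.

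Then:

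- Do not enter different outcomes as levels of one factor.
- If ANCOVA on the post value with baseline as covariate is preferred, pre-specify it as the single treatment test in place of the interaction, not alongside it.
- State what the Bonferroni correction covers, since time has only one pair (for example, the set of outcomes), and which contrast Cohen's d describes.
- Compare audible with non-audible manipulation in a separate model within the intervention group. Label it a non-randomised comparison, because these subgroups are defined after allocation.

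With two recordings, the cost is SAP wording only and no new data. If a third recording is planned, the study sequence must also describe it and its timing, the time factor must list all three levels, and the cost is then more than wording.

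### The SAP does not say which contrast tests the treatment effect and leaves the pre-randomisation value out of the model, where ANCOVA would usually be more precise

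*Combined protocol and SAP*

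**What the plan says.** The section Statistical Analysis Plan (SAP) specifies one inferential model: "A repeated measures ANOVA model will be applied with the variable of interest as the within-subjects factor (three levels) and the group"; group, with two levels, enters between subjects. The section continues: "Bonferroni correction will be used for two-to-two comparisons". It does not say which pairs are meant. No interaction, main effect or particular pair is named as the test of the treatment effect, and no covariate is listed.

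The specific objectives are framed as comparisons between groups. The baropodometric one reads: "To assess the changes in the variables % weight load, bearing surface and maximum pressure in both feet by baropodometry between the intervention group", with control as the comparator; the stabilometric one is parallel.

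The procedure gives each participant two recordings. The first is taken at step 5 of the study sequence ("The assessor shall collect data to obtain the independent variables of stabilometry and baropodometry by means of standardised recording on the measurement platform"). Randomisation follows at step 6, and the text before the sequence confirms the order: "After the data collection, a randomization (Epidat V4.0) of the selected subjects will be carried out". After treatment comes the second and last recording, at step 8: "The patient will return to the assessment room with the assessor for data collection to obtain the variables of stabilometry and baropodometry".

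**The concern.** There are two linked problems.

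**No contrast is fixed.** A repeated-measures ANOVA with a group factor prints a within-subjects effect, a group effect, an interaction and whatever pairwise comparisons are requested. These answer different questions. If the within-subjects factor is time with two levels, the interaction estimates the treatment difference. The group main effect averages the two occasions and, because the arms do not differ in expectation before treatment, estimates half of it. A pre-post comparison inside one arm is not a randomised comparison. The SAP does not say that either of the last two will be read as the treatment effect, but nothing in it rules that out.

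**The baseline is not used as a covariate.** A value taken before randomisation is available for every outcome. The change-score comparison uses it with a fixed slope of 1, whereas ANCOVA estimates the slope and usually gives a narrower interval from the same data.

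What is at stake is efficiency and prior commitment, not bias.

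**Working it through.** The documents give no sample size, power, SD, correlation or target effect, so there is no planned figure to reproduce. The results below are ranges under stated assumptions.

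**Inputs from the documents**
- Two recordings per participant, the first before randomisation (study sequence, steps 5, 6 and 8).
- Two groups (SAP).
- Two-sided 5% level, inferred from "a 95% confidence interval will be applied in all statistical tests"; sidedness is not stated.
- d = 0.5, taken only because it is the SAP's own benchmark for a moderate effect. The SAP sets no target.

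**Assumptions**
- The within-subjects factor is time, with two levels.
- n per arm, equal allocation, normal outcomes.
- Equal pre and post SD σ (relaxed below), pre-post correlation ρ from 0.3 to 0.9.
- d is in units of σ.

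**Formulas**
- Interaction (change-score difference): variance = 2(1−ρ)σ² × 2/n.
- ANCOVA: variance = (1−ρ²)σ² × (2/n) × (2n−3)/(2n−4). The last factor is the cost of estimating the slope.
- Ratio, ANCOVA to interaction: [(1+ρ)/2] × (2n−3)/(2n−4), which tends to (1+ρ)/2 in large samples.
- Break-even: the ratio equals 1 at ρ = (2n−5)/(2n−3).
- Power: noncentral t, with 2n−3 df for ANCOVA and 2n−2 for the interaction.

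As an example, at n = 30 and ρ = 0.5 the ratio is 0.75 × 57/56 = 0.76.

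**Results at d = 0.5** (paired entries are ANCOVA / interaction)

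| ρ | Large-sample ratio | Ratio, 30 per arm | Power, 30 per arm | Power, 15 per arm | n per arm for 80% power |
|---|---|---|---|---|---|
| 0.3 | 0.65 | 0.66 | 51% / 36% | 27% / 20% | 59 / 89 |
| 0.5 | 0.75 | 0.76 | 59% / 48% | 32% / 26% | 49 / 64 |
| 0.7 | 0.85 | 0.87 | 75% / 69% | 44% / 40% | 34 / 39 |
| 0.8 | 0.90 | 0.92 | 88% / 85% | 58% / 55% | 25 / 27 |
| 0.9 | 0.95 | 0.97 | 99% / 99% | 84% / 84% | 14 / 14 |

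**Where the gain stops.** Break-even ρ is 15/17 = 0.88 at 10 per arm, 25/27 = 0.93 at 15, 35/37 = 0.95 at 20 and 55/57 = 0.96 at 30. At 10 per arm and ρ = 0.9 the ratio is 0.95 × 17/16 = 1.01, so ANCOVA is marginally worse there.

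**Unequal SDs.** With k = post/pre SD, the large-sample ratio is (1−ρ²)k²/(1+k²−2ρk). Over the same ρ values it is 0.50 to 0.64 at k = 0.8 and 0.78 to 1.00 at k = 1.25. It equals 1 only where ρk = 1, for example k = 1.25 with ρ = 0.8.

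**Group main effect.** Averaging two occasions gives per-participant variance σ²(1+ρ)/2 and an expected difference of (0 + 0.5)/2 = 0.25. At 30 per arm and ρ = 0.5 its power is about 20%, against 48% for the interaction and 59% for ANCOVA.

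**Simulation check.** With 40,000 trials per cell at 30 per arm and ρ = 0.3/0.5/0.7/0.8/0.9, power was 50.7/58.6/75.3/88.1/99.2% for ANCOVA and 36.0/47.8/69.2/85.3/99.0% for the interaction. Mean estimates were 0.50 for both, which confirms that the interaction is unbiased, and 0.25 for the group main effect.

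**The case against.** The strongest reply is that a change-score analysis is not an error. Under randomisation the interaction is valid and unbiased, and it already uses the baseline through the change. The objectives speak of changes between groups, which points to the interaction, and no text says a main effect or a within-arm test will be reported as the treatment effect. All of this is correct, and it is why the point is one of efficiency and commitment.

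The size of the gain also cannot be fixed. The large contrasts come from ρ = 0.3, and nothing in the documents favours that over 0.9. The two recordings are made before and after a single intervention, so a high correlation cannot be excluded. At ρ = 0.8 the gain is about 3 points of power at 15 or 30 per arm; at 0.9 it is practically nil. This limits how much weight the precision argument can bear, and it stands.

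Finally, the calculations describe a two-level time factor. The SAP calls the factor the variable of interest and gives it three levels. It might mean three occasions, which would make the interaction a 2-df test, or the three variables listed for each device, in which case there is no time factor. That objection is fair to the arithmetic, but it strengthens the first half of the point: from the SAP one cannot establish that a group-by-time term exists, let alone that it is the test.

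The audible versus non-audible comparison lies outside this argument, because those subgroups form after randomisation. So does the choice of a primary outcome.

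**Conclusion.** The concern holds. The SAP names no contrast as the test of the treatment effect and includes no baseline covariate, although a pre-randomisation value is collected for every outcome. Both statements rest on the text alone.

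The precision gain from ANCOVA depends on quantities the documents do not give. With two occasions and equal SDs it ranges from a 35% reduction in variance (1 − 0.65) at ρ = 0.3 to 5% (1 − 0.95) at ρ = 0.9 in large samples. It disappears at very high correlation in small arms. The word is therefore usually, not always. No bias is claimed against the interaction. The change should be made: it improves the randomised comparison at almost no cost and settles in advance which estimate answers the objectives.

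**What to change.** - For each outcome, specify as the main analysis an ANCOVA of the post-treatment value on group, with the same participant's pre-treatment value as covariate.
- State that the efficacy conclusion rests on the adjusted between-group difference with its 95% CI.
- Report within-arm pre-post changes as descriptive only.
- If a repeated-measures ANOVA is kept, name its within-subjects factor and reconcile the three levels with the two recordings. If the interaction is preferred to ANCOVA, it must still be named as the test.

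The cost is SAP wording and one degree of freedom per model. The analysis runs in the general linear model procedure of the SPSS package already specified, and no new data are needed.

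### No outcome is primary and no adjustment is stated across six to eight equally ranked outcomes: if any one significant result counted, family-wise error would be about 26–34% with independent tests, and less with correlated ones

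*Combined protocol and SAP*

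**What the plan says.** The general objective covers both measurement domains at once: "The main objective of this study was to evaluate, in healthy individuals, the stabilometric and baropodometric modifications recorded after an osteopathic tug manipulation". The specific objectives then set out the stabilometric comparison, "modifications in the variables of oscillation in X axis, oscillation in Y axis and ellipse area between the intervention group and the control group", and the baropodometric one, "To assess the changes in the variables % weight load, bearing surface and maximum pressure in both feet by baropodometry". A third specific objective compares subgroups of the intervention arm: "audible and non-audible manipulation and to compare the results". Nothing ranks these variables or calls one primary.

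The data list under Baropodometric and stabilometric assessment has six entries, three per domain. Support area is in the singular ("Area of support of the foot"), as is the point of maximum pressure. Only load share is given for each foot.

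Outcomes are recorded twice. Step 5 of the study sequence, before randomisation, reads "The assessor shall collect data to obtain the independent variables of stabilometry and baropodometry". Step 8, after the intervention, calls for "data collection to obtain the variables of stabilometry and baropodometry by standardised recording on the measurement platform, as was done previously".

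The SAP specifies a repeated measures ANOVA. The variable of interest is a within-subjects factor with three levels, and group is a between-subjects factor with two. Bonferroni is applied to pairwise comparisons, and "a 95% confidence interval will be applied in all statistical tests". The SAP does not say which ANOVA effect answers the objectives, gives no rule across outcomes, and does not define a positive result.

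**The concern.** With two groups there is only one between-group pair, so a pairwise Bonferroni correction leaves that contrast unchanged. No sentence extends it from one outcome to the next. As written, each outcome can be tested at its own 5% level.

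Two things are at stake. First, the more outcomes are tested this way, the more likely it is that at least one is significant when the technique does nothing. Second, with no primary outcome, a reader of the results cannot tell which variable was meant to carry the conclusion, so selection after seeing the data cannot be ruled out. The second problem exists whatever the number of outcomes or their correlation.

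**Working it through.** The documents give no family-wise error rate, sample size or power, so there is no figure to reproduce.

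**Inputs**
- Per-test level: 0.05, inferred from the 95% level in the SAP. Two-sided testing is assumed because sidedness is not stated.
- Stabilometric outcomes: 3 (Objectives, Specific).
- Baropodometric outcomes: 3 if counted as in the data list. If the feet are analysed separately there are 5: support area on two feet, maximum pressure on two feet, and load share once. If left and right load shares sum to 100 (assumed), their two tests give the same p-value.
- Total: 3 + 3 = 6 to 3 + 5 = 8 distinct outcomes. The audible/non-audible comparison is not counted.
- Correlations between outcomes: not given, so a range is assumed.

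**One between-group test per outcome, independent**

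Family-wise error = 1 − (1 − 0.05)^k
- k = 6: 1 − 0.95^6 = 0.265
- k = 8: 1 − 0.95^8 = 0.337

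**Same, with a common correlation ρ between all test statistics**

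Family-wise error = 1 − ∫ φ(u) [Φ((c − √ρ u)/√(1 − ρ)) − Φ((−c − √ρ u)/√(1 − ρ))]^k du, with c the two-sided 5% normal critical value, by numerical integration.

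| Assumed ρ | k = 6 | k = 8 |
|---|---|---|
| 0.3 | 24.1% | 30.0% |
| 0.5 | 20.7% | 25.0% |
| 0.7 | 16.4% | 19.1% |
| 0.9 | 10.8% | 11.9% |

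**Correlation within each domain only (0.3–0.9), domains independent**

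Family-wise error = 1 − (1 − F_stabilometric)(1 − F_baropodometric), where F is the error within one domain.
- Six outcomes (3 + 3): at 0.3, 1 − (1 − 0.1362)² = 0.254; at 0.9, 1 − (1 − 0.0836)² = 0.160.
- Eight outcomes (3 + 5): at 0.3, 1 − (1 − 0.1362)(1 − 0.2089) = 0.317; at 0.9, 1 − (1 − 0.0836)(1 − 0.1016) = 0.177.

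**One model per domain**

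The SAP's three-level factor could mean the three variables of a domain, giving one model per domain. If individual variables are followed up only after a significant group-related test in that domain, there are two gatekeeping tests. With no effect on any outcome and the two tests independent, the error is at most 1 − 0.95^2 = 0.0975.

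**Which reading applies**

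The text does not settle it. Three levels cannot be time points under the described schedule, which has two recordings (steps 5 and 8). Three variables would fit the count in each domain, but then the two recordings have no place in the model as stated.

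**The case against.** The strongest reply is that the harm is conditional. The plan sets out to evaluate changes in healthy people, states no success rule, and does not say that one significant variable would prove an effect. This stands: the percentages apply only to an any-one-counts reading. They are not the false-positive rate of a conclusion that the plan commits to.

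A second reply is that the outcomes are correlated and that the SAP, read literally, may intend one model per domain. This also stands as a limit on size. It lowers the figure to about 10% on that reading, still above 5%. The assumed correlations have no support in the documents; a common 0.9 across sway, load share and pressure is there only to bound the range.

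Two other readings are tempting.
- A reader might count nine outcomes from the reference to both feet and arrive at 37% (1 − 0.95^9). That requires left and right load share to be two distinct tests. As percentages of body load on each foot they naturally sum to 100, although the documents do not say so.
- A reader might take the three levels to mean that every group contrast is tested at 0.05/3, which would give about 4–14% for six to nine outcomes at correlations from 0.9 down to none. No text does this. If three variables form the within-subjects factor, its pairs set variable against variable, and correcting those does not change the level of the group test.

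The study cannot be excused as exploratory on its own wording: in the SAP that term describes data checking and cleaning, while the objectives compare an intervention with a control group.

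**Conclusion.** The concern holds in this form. No outcome is primary, all tests use the 95% level, and the only stated correction is not said to act across outcomes. With six to eight distinct outcomes, one two-sided 0.05 test each, and any single significant result taken as an effect, the family-wise error is about 26–34% if the tests are independent. It is about 11–30% at assumed common correlations of 0.9 down to 0.3. Under a gated one-model-per-domain reading it is up to about 10%.

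These sizes rest on an inferred two-sided level, an inferred count of outcomes, assumed correlations, and a success rule that the plan does not state. The absence of a primary outcome rests on none of these. The plan should be changed, with medium confidence as to the size of the problem.

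**What to change.** 1. Reconcile the three-level within-subjects factor in the SAP with the two recordings in steps 5 and 8.
2. Before group results are seen, name either one primary outcome tested at 5%, or one per domain at 2.5% each (0.025 + 0.025 = 0.05). The choice is the sponsor's. The second option respects a main objective that names both domains and avoids a null result in one blocking every claim in the other.
3. State that the test is the group-by-time interaction, which with two recordings is the between-group difference in pre-to-post change.
4. Report the remaining outcomes with 95% confidence intervals and no efficacy claim, or test them by Holm behind a gate. With one primary, proceed only if it is significant. With one per domain, apply Holm at 2.5% within a domain only if that domain's primary is significant. The gate matters: a primary at 5% plus an ungated Holm family at 5% could reach 1 − 0.95^2 = 9.75% if independent.
5. Report the audible/non-audible comparison with 95% confidence intervals and no efficacy claim.
6. State whether the feet are analysed separately, and test load share once.

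**Cost.** SAP wording only; no extra measurements. Non-primary outcomes face stricter thresholds or carry no confirmatory claim. With one primary, the first Holm step is 0.05/5 = 0.010 for six outcomes or 0.05/7 = 0.0071 for eight. With one per domain, it is 0.025/2 = 0.0125 for two remaining outcomes or 0.025/4 = 0.00625 for four. No sample size is given, so precision for the chosen primary is unknown. The documents mix past and future tense, so they do not show whether the change can still be made before results are seen.
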